7.2.3 Definition of Response and progression

PFS6 is the primary endpoint for Group C. Additionally; several secondary endpoints are based on neuroimaging as assessed by MRI: the response rate, median progression-free survival, and the progression-free survival at defined time points. The sites should base their estimate of response according to the RANO criteria (Ref. 36) which would also be state of the art outside a clinical trial. The subsequent MRIs will be compared to the baseline MRI as defined in Section 7.2.5. In brief, the following definitions apply:

- **Complete Response (CR):** complete disappearance of all enhancing measurable and nonmeasurable disease sustained for at least 4 weeks; no new lesions; stable or improved nonenhancing (T2/FLAIR) lesions; patients must be off corticosteroids (or on physiologic replacement doses only); and stable or improved clinically. Note: Patients with nonmeasurable disease only cannot have a complete response; the best response possible is stable disease.
- **Partial Response (PR):** 50% decrease compared with baseline in the sum of products of perpendicular diameters of all measurable enhancing lesions sustained for at least 4 weeks; no progression of nonmeasurable disease; no new lesions; stable or improved nonenhancing (T2/FLAIR) lesions on same or lower dose of corticosteroids compared with baseline scan; the corticosteroid dose at the time of the scan evaluation should be no greater than the dose at time of baseline scan; and stable or improved clinically. Note: Patients with nonmeasurable disease only cannot have a partial response; the best response possible is stable disease.
- **Stable disease (SD):** does not qualify for complete response, partial response, or progression; stable nonenhancing (T2/FLAIR) lesions on same or lower dose of corticosteroids compared with baseline scan. In the event that the corticosteroid dose was increased for new symptoms and signs without confirmation of disease progression on neuroimaging, and subsequent follow-up imaging shows that this increase in corticosteroids was required because of disease progression, the last scan considered to show stable disease will be the scan obtained when the corticosteroid dose was equivalent to the baseline dose.
- **Progression (PD):** 25% increase in sum of the products of perpendicular diameters of enhancing lesions compared with the smallest tumor measurement obtained either at baseline (if no decrease) or best response, on stable or increasing doses of corticosteroids; significant increase in T2/FLAIR nonenhancing lesion on stable or increasing doses of corticosteroids compared with baseline scan or best response after initiation of therapy; any new lesion; clear clinical deterioration not attributable to other causes apart from the tumor (e.g., seizures, medication

adverse effects, complications of therapy, cerebrovascular events, infection, and so on) or changes in corticosteroid dose; failure to return for evaluation as a result of death or deteriorating condition; or clear progression of nonmeasurable disease.

The measures previously proposed by RANO (Ref. 36) to measure the clinical deterioration will also be completed and a comparison of both clinical and radiological evaluation will be made.

RANO clinical evaluation will be based on KPS evaluation. Clinical progression is defined as the presence of the following conditions

- a decline in KPS from 100 or 90 to 70 or less, or
- a decline in KPS of at least 20 from 80 or less, or
- a decline in KPS from any baseline to 50 or less, for at least 7 days,

will be considered neurologic deterioration unless attributable to comorbid events or changes in corticosteroid dose.

Criterion	CR	PR	SD	PD
T1 gadolinium enhancing disease	None	$\geq 50\% \downarrow$	$< 50\% \downarrow$ but $< 25\% \uparrow$	$\geq 25\% \uparrow$
T2/FLAIR	Stable or \downarrow	Stable or \downarrow	Stable or \downarrow	\uparrow
New lesion	None	None	None	Present
Corticosteroids	None	Stable or \downarrow	Stable or \downarrow	Not applicable*
Clinical status	Stable or \uparrow	Stable or \uparrow	Stable or \uparrow	\downarrow
Requirements for response	All	All	All	Any

*increase in steroids alone does not qualify for PD

For this trial, the primary measure of response and progression will be determined by the locally assessed response according to the RANO criteria. All treatment decisions should be based on the RANO criteria.

7.2.4 Neurological evaluation

Neurological evaluation will be performed using NANO scale.

The NANO criteria will be determined as follows (Ref. 19):

- *Neurologic response* is defined as a ≥ 2 level improvement in at least one domain without worsening in other domains from baseline or best level of function that is not attributable to change in concurrent medications or recovery from a comorbid event.
- *Neurologic stability* indicates a score of neurologic function that does not meet criteria for neurologic response, neurologic progression, non-evaluable, or not assessed.
- *Neurologic progression* is defined as a ≥ 2 level worsening from baseline or best level of function within ≥ 1 domain or worsening to the highest score within ≥ 1 domain that is felt to be related to underlying tumor progression and not attributable to a comorbid event or change in concurrent

medication. Of note, an assessment of neurologic progression does not require evaluation of a minimum number of domains of the NANO scale if any of these conditions is met.

- *Non-evaluable* should be selected if it is more likely than not that a factor other than underlying tumor activity contributed to an observed change in neurologic function. Such factors may include changes in a concurrent medication, such as corticosteroids, sedatives, narcotics, or anti-epileptic agents; acute or chronic adverse events related to therapeutic interventions; or a comorbid event such as a toxic-metabolic encephalopathy, post-ictal state, stroke, etc. Non-evaluable could also be selected if measurement of a given domain is not feasible due to an alteration of another domain. For example, assessment of upper extremity ataxia may not be possible if weakness of the extremity limits mobility. In this case, the strength domain should be assigned a numeric score but the upper extremity ataxia domain would be scored as non-evaluable.
- *Not assessed* should be scored if the clinician omits evaluation of that particular domain during his/her examination. If a particular domain is marked not assessed at baseline, then that domain cannot thereafter be considered for progression or response. In general, assessment and scoring of all domains is encouraged.

Neurologic Assessment in Neuro-Oncology will be based on NANO scale.

7.2.5 MRI evaluation

Follow up assessments will be done using modified RANO (while considering T2/FLAIR).

- Only contrast-enhancing MRI lesions with two perpendicular diameters of 10 mm or more visible on 2 or more axial slices which are not more than 5 mm apart are eligible as target lesions.
- In most patients, only one lesion will be present. In case of multifocal measurable disease, a minimum of 2 and maximum of 5 largest enlarging lesions will be chosen as target lesions and the sum of the products of the perpendicular diameters will be determined.
- All other lesions that do not meet the criteria for target lesions are defined as non-target lesions and are assessed according to the same schedule. They are only taken into account in two situations:
 - if one of them clearly progresses, the overall response to therapy will be evaluated as "progression", independent of the response of target lesions.
 - all lesions must have completely disappeared to report a "complete response".
- Adequate investigations must be carried out at each evaluation of the disease to detect new lesions. If any new lesion is found, the response will be evaluated as "progression". Regardless of the status of enhancing lesions, if progressive lesions are observed on T2-weighted images or FLAIR images, the patient will be considered radiologically progressive, but treatment may continue if this is considered to be in the best interest of the patient and there are no signs or symptoms of clinical progression.
- Postoperative changes on contrast-enhanced neuro-imaging may interfere with disease evaluation. Within the first three days after surgery on MR imaging a thin linear enhancement may develop around the resection cavity, thereafter this enhancement may become thick and nodular. Enhancement of dural and meninges may be more pronounced, even within the first days. The postoperative linear enhancement may persist up to 3-6 months, dural and meningeal enhancement may last much longer. If MRI obtained within 72 hours after surgery shows enhancing lesions with a nodular or mass-like appearance in areas showing tumor on the pre-operative scans this is highly suggestive of residual tumor. The use of diffusion-weighted MR imaging in the immediate postoperative MRI may help with the identification of ischemic areas around the surgical cavity that may show enhancement with further follow-up.

Follow up assessments will be done using RANO criteria (while considering T2/FLAIR).

Baseline evaluations:

- Group A and B: baseline MRI is defined as MRI done within 14 days of first dose of TG02. If a 72-hour post-surgery MRI was done and falls within this time window, baseline MRI does not need to be repeated.
- Group C: baseline MRI is defined as MRI done within 14 days of first dose of TG02. For patients with surgery for recurrence, if a 72-hour post-surgery MRI was done and falls within this time window, baseline MRI does not need to be repeated.

MRI Response criteria:

The sites should base their estimate of response on the RANO criteria (Ref. 36) (also considering T2 weighted and FLAIR images), which would also be state of the art outside a clinical trial. In brief, the following definitions apply:

Complete response (CR):

Requires all of the following:

1. complete disappearance of all enhancing measurable and non-measurable disease sustained for at least 4 weeks; no new lesions;
2. stable or improved non-enhancing (T2/FLAIR) lesions;
3. patients must be off corticosteroids (or on physiologic replacement doses only);
4. and stable or improved clinically.

Note: Patients with non-measurable disease only cannot have a complete response; the best response possible is stable disease.

Partial response (PR):

Requires all of the following:

1. 50% decrease compared with baseline in the sum of products of perpendicular diameters of all measurable enhancing lesions sustained for at least 4 weeks;
2. no progression of non-measurable disease;
3. no new lesions;
4. stable or improved non-enhancing (T2/FLAIR) lesions on same or lower dose of corticosteroids compared with baseline scan;
5. the corticosteroid dose at the time of the scan evaluation should be no greater than the dose at time of baseline scan; and stable or improved clinically.

Note: Patients with non-measurable disease only cannot have a partial response; the best response possible is stable disease.

Progressive disease (PD):

Progression is defined by any of the following:

1. 25% increase in sum of the products of perpendicular diameters of enhancing lesions compared with the smallest tumor measurement obtained either at baseline (if no decrease) or best response, on stable or increasing doses of corticosteroids;

2. significant increase in T2/FLAIR nonenhancing lesion on stable or increasing doses of corticosteroids compared with baseline scan or best response after initiation of therapy not caused by comorbid events (e.g., radiation therapy, demyelination, ischemic injury, infection, seizures, postoperative changes, or other treatment effects);

3. any new lesion; clear clinical deterioration not attributable to other causes apart from the tumor (e.g., seizures, medication adverse effects, complications of therapy, cerebrovascular events, infection, and so on) or changes in corticosteroid dose;

4. failure to return for evaluation as a result of death or deteriorating condition; or clear progression of non-measurable disease.

Based on the RANO criteria, for the determination of first progression in Group A, after initial radiotherapy plus TG02, the following criteria should be used in addition to those above:

Progressive disease less than 12 weeks after completion of radiotherapy

Progression can only be defined using diagnostic imaging if there is new enhancement outside of the radiation field (beyond the high-dose region or 80% isodose line) or if there is unequivocal evidence of viable tumor on histopathologic sampling (e.g., solid tumor areas i.e., 70% tumor cell nuclei in areas, high or progressive increase in MIB-1 proliferation index compared with prior biopsy, or evidence for histologic progression or increased anaplasia in tumor). Note: Given the difficulty of differentiating true progression from pseudoprogression, clinical decline alone, in the absence of radiographic or histologic confirmation of progression, will not be sufficient for definition of progressive disease in the first 12 weeks after completion of concurrent chemoradiotherapy.

Progressive disease 12 weeks or more after radiotherapy completion

1. New contrast-enhancing lesion outside of radiation field on decreasing, stable, or increasing doses of corticosteroids.

2. Increase by 25% in the sum of the products of perpendicular diameters between the first postradiotherapy scan, or a subsequent scan with smaller tumor size, and the scan at 12 weeks or later on stable or increasing doses of corticosteroids.

3. Clinical deterioration not attributable to concurrent medication or comorbid conditions is sufficient to declare progression on current treatment but not for entry onto a clinical trial for recurrence.

4. For patients receiving antiangiogenic therapy, significant increase in T2/FLAIR nonenhancing lesion may also be considered progressive disease. The increased T2/FLAIR must have occurred with the patient on stable or increasing doses of corticosteroids compared with baseline scan or best response after initiation of therapy and not be a result of comorbid events (e.g., effects of radiation therapy, demyelination, ischemic injury, infection, seizures, postoperative changes, or other treatment effects).

If the evidence of PD is equivocal (target or non-target lesions), treatment may continue until the next assessment, but if PD is confirmed at the next follow-up, the earlier date must be used as the date of progression.

In case non-measurable tumor is left after surgery i.e. tumor less than 10x10 mm, unequivocal progression of non-target lesion may be accepted as evidence of disease progression, where the overall tumor burden has increased sufficiently to merit discontinuation of treatment. Modest increase in the size of a non-target lesion is NOT considered unequivocal progression. If the evidence of PD is equivocal (target or non-target), treatment may continue until the next assessment, but if confirmed, the earlier date must be used as the date of progression. This implies that in case of gross total resection of the

enhancing lesion, if at follow up minimal enhancement of unclear significance arises, treatment may continue until further follow-up gives unequivocal evidence of tumor progression.

Stable Disease (SD):

This occurs if the patients did not qualify for complete response, partial response, or progression (see above) and requires: 1) No meaningful change in the appearance of the FLAIR/T2 images compared to baseline or to the nadir (point with the smallest FLAIR/T2 abnormalities) if a decrease occurred.

Evaluation of response, treatment decision and central review:

- For this trial, the primary measure of response and progression will be determined by the locally assessed response according to the RANO criteria. The time point of progression will be determined at the sites, although the centers in Zurich and Vienna (Reference Neuroradiology) will be happy to provide support.
- Study treatment is completed at the time of first progression. Follow-up until death or the end of data acquisition is required within this trial.
- To ensure a homogeneous radiological evaluation, all MRI images will be retrospectively centrally reviewed by Vienna [REDACTED] study coordinator, study co-coordinator and Tragara pharmaceuticals representative as a secondary analysis and specific study MRI protocol will be used.

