16.5.1.4 Central review

A Blinded Independent Central Review (BICR) will be organized retrospectively to review all collected scans in this study.

The BICR will remain blinded regarding the treatment group of the patients. Furthermore, the reviewers will be blinded regarding the site's assessment which will only be unblinded to the study coordinator.

BICR ensures an independent evaluation of patient scans in a specific study by experts in the specific imaging modality. For further details about the Independent Central Review, please refer to the Central Review Charter, that will be provided as a separate guidelines document.

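### Section 7.2.5 gives Group A two conflicting progression rules after radiotherapy and does not say which one governs PFS

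*Combined protocol and SAP*

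**What the plan says.** The general definition in section 7.2.5 reads "Progression is defined by any of the following". Its first item is a "25% increase in sum of the products of perpendicular diameters of enhancing lesions compared with the smallest tumor measurement obtained either at baseline" or best response. Any new lesion, and clear clinical deterioration not explained by other causes, form item 3. Section 7.2.3 gives the same definition with no Group A exception and adds: "The subsequent MRIs will be compared to the baseline MRI as defined in Section 7.2.5".

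For first progression in Group A, section 7.2.5 then states that "the following criteria should be used in addition to those above". What follows is narrower than the general list:

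- **Before 12 weeks after radiotherapy (RT), imaging.** "Progression can only be defined using diagnostic imaging if there is new enhancement outside of the radiation field", or on histological proof of viable tumour.
- **Before 12 weeks, clinical decline.** Without radiographic or histological confirmation it "will not be sufficient for definition of progressive disease in the first 12 weeks" after RT. Difficulty in telling progression from pseudoprogression is given as the reason.
- **From 12 weeks.** The 25% increase is measured from the first post-RT scan, or a later smaller one.

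PFS and PFS-6 rest on the investigator's assessment (section 7.2.2). For Group A both are secondary endpoints (2.2.2), analysed descriptively (8.2.2).

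**The concern.** A restriction added to a list in which any single item suffices cannot cancel a progression that the list has already declared. The connecting phrase therefore works against the content of the rules it introduces, and nothing says which prevails. Two investigators with the same scans could follow the protocol and record different progression dates.

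The stake is Group A PFS-6 and median PFS. If sites follow the general list, treatment-related enhancement after RT counts as an event and both estimates are biased downwards. If sites differ, the estimates mix two definitions and cannot be compared cleanly with outside data. Section 7.2.5 also ends study treatment at first progression, so the same ambiguity reaches the treatment text.

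**Working it through.** The plan states no figure for Group A PFS, so there is none to reproduce. The check sets the rules side by side, places the scans in time, and sizes the effect.

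**1. The two rule sets**

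| Finding | General list (7.2.3, 7.2.5) | Group A rules (7.2.5) |
|---|---|---|
| In-field rise of 25% or more, under 12 weeks after RT | Progression (item 1) | Not progression without histology |
| New in-field enhancement, under 12 weeks | Progression if read as a new lesion (item 3) | Not progression without histology |
| Clinical decline alone, under 12 weeks | Progression (item 3) | Not sufficient |
| 25% rise, from 12 weeks | Against baseline or nadir | Against first post-RT scan or later smaller scan |

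The Group A baseline is a pre-RT scan: the MRI is taken within 14 days before the first TG02 dose (3.1), and RT starts on the day of that dose (5.7).

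**2. Timing of the scans**

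Inputs: 28-day cycles; MRI every 2 cycles ± 8 days (6.2.4.2), taken to fall at Day 1 of the next cycle; 15 weekday fractions within Days 1-21 (5.2.1.1, 5.7), so RT ends on Day 19-21.

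- Scan 1: 2 × 28 + 1 = Day 57, window Day 49-65. Weeks after RT: (49 − 21)/7 = 4.0 to (65 − 19)/7 = 6.6.
- Scan 2: 4 × 28 + 1 = Day 113, window Day 105-121. Weeks after RT: (105 − 21)/7 = 12.0 to (121 − 19)/7 = 14.6.

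Scan 1 is always inside the 12-week window. Scan 2 falls where the reference scans differ. If RT ends 7 days late, as 5.7.8 permits, and the cycles do not shift, scan 2 falls at (105 − 28)/7 = 11.0 to (121 − 26)/7 = 13.6 weeks and straddles the boundary.

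**3. An invented series**

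Sums of products: 400 before RT, 520 at scan 1 (in-field), 530 at about week 13.

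- Scan 1: 520/400 − 1 = +30%. General list: progression. Group A rule: not progression.
- Scan 2, general list: 530/400 − 1 = +32.5%, progression.
- Scan 2, Group A rule: 530/520 − 1 = +1.9%, not progression.

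The two rule sets disagree at both scans.

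**4. Size**

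One patient of 24 is 100/24 = 4.2 points of PFS-6, treating the Kaplan-Meier estimate as a simple proportion (no censoring before 6 months). The documents give neither a pseudoprogression rate nor an expected PFS-6 for Group A. Assume a true PFS-6 of p, and that a share r of the patients who are truly progression-free at 6 months is scored as progressed early. The loss is p × r.

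| Assumed p | Assumed r | Loss in PFS-6 | Patients of 24 |
|---|---|---|---|
| 0.30 | 0.10 | 3 points | 0.7 |
| 0.40 | 0.20 | 8 points | 1.9 |
| 0.50 | 0.30 | 15 points | 3.6 |

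**The case against.** The best defence is that the Group A text is plainly restrictive and names pseudoprogression as its reason, so a sensible investigator would treat it as an override. On that view the additive phrase only preserves general items that the Group A rules leave alone, such as T2/FLAIR increase or failure to return. A reader might otherwise infer that the plan counts pseudoprogression as progression. The documents do not support that: they contain an unresolved contradiction, and the override is probably what was meant. But it is not stated, and 7.2.3 repeats the general list unqualified.

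There are also safeguards. Section 7.1.8 recommends continuing treatment and repeating the MRI when progression is unclear, and 7.2.5 allows continuation when the evidence is equivocal. General item 2 excludes radiation effects, and item 3 excludes complications of therapy. These help only in part. They cover unclear cases, the enhancement item has no such exclusion, and progression confirmed at the next scan is back-dated to the earlier one. In the invented series, a reader who called scan 1 equivocal and followed the general list would still date progression to scan 1.

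A reader might also infer that central review drives the problem, since "The BICR will remain blinded regarding the treatment group of the patients" and such a reader cannot tell which patients the Group A rules cover. That does not follow for the planned analysis. PFS is investigator-assessed in an open-label trial, central review is a secondary analysis, and section 8.2.2 plans centrally reviewed PFS estimates only under Group C.

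**Conclusion.** The contradiction is real and needs resolving. Patients with an in-field rise, a new in-field lesion or clinical decline alone within 12 weeks of RT can be scored either way. So can patients whose later scans exceed the pre-RT baseline by 25% but not the first post-RT scan. Each such patient who would otherwise be progression-free at 6 months moves PFS-6 by about 4 points. The range of about 3-15 points rests wholly on the assumed 10-30% rate and assumed true PFS-6 of 30-50%.

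Three stronger readings fail:

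- An effect of 10-30 points would require every affected patient to be otherwise progression-free at 6 months.
- The conflict does not decide the first scan of every Group A patient, only of those with one of the triggers above.
- Duration of response is barely touched: a responder's nadir is already a post-RT scan, so both 25% rules then use the same reference.

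Group A PFS is secondary and descriptive. The DLT-based dose decision and the Group C primary test do not depend on it.

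**What to change.** Reconcile sections 7.2.3 and 7.2.5. State that, for the Group A PFS endpoints, the post-RT rules take precedence wherever they conflict with the general enhancement, new-lesion and clinical-deterioration items, including the reference scan from 12 weeks. State also that the general items they do not address (T2/FLAIR, non-measurable disease, death or failure to return) stay in force. Replacing the general list wholesale would go too far, because it would drop those items. Add a cross-reference from 7.2.3.

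The passages that tie treatment decisions to the same criteria (7.2.3) and end study treatment at first progression (7.2.5) must be reconciled with this wording. Which clinical rule applies is for the sponsor and investigators to decide; no position is taken here.

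Only if a centrally reviewed Group A PFS is to be reported, give that reader the Group A status, the RT end date and the RT field. Radiotherapy dosimetry and treatment data are already collected for Group A under section 16.5.2. In that case the central review charter needs a matching line.

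The cost is protocol wording. No new data, visits or patients are needed.

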These estimates will be presented both based on investigator and centrally reviewed progression data.

- Overall survival

In the efficacy population:

The OS rate at 9 months (OS-9), 1 year (OS-12) and the median will be extracted from the Kaplan-Meyer OS curve. For OS-9 and OS-12 95% two-sided confidence intervals will be computed based on Greenwood's formula. For the median the Reflected Method will provide 95% two-sided confidence intervals.

- Response and duration of response

In the efficacy population:

The best overall response will be presented in contingency table with numbers and percentages. The objective response (CR+PR) and complete response (CR) rates will be reported with exact (binomial) 95% two-sided confidence interval.

Duration of objective response and complete response will be estimated using Kaplan-Meier methodology. Median duration of objective and complete response with corresponding 95% two-sided confidence interval provided by the Reflected Method will be displayed.

These estimates will be presented both based on investigator and centrally reviewed response data.

- Success rate

In the efficacy population:

The success rate will be reported with exact (binomial) 95% two-sided confidence interval.

Success rate will be presented both based on investigator and centrally reviewed response data.

- Neurologic progression free survival

In the efficacy population:

The NPFS rate at 6 months (NPFS6) and the median NPFS will be extracted from the Kaplan-Meyer PFS curve. For NPFS6, 95% two-sided confidence intervals will be computed based on the Greenwood's formula. For the median the Reflected Method will provide 95% two-sided confidence intervals.

- Comparison of PFS by local investigator and by central review and comparison of NPFS and CDFS.

In the efficacy population:

The differences of times to event between these estimates will be tabulated.

- Safety and tolerability

In the safety population:

The safety and tolerability analyses will be presented at baseline and up to 30 days after the last administration of study drug. Baseline will include all information recorded up to the nearest date prior to or at randomization. Exceptionally in absence of this assessment, the first assessment performed after randomization but before start of protocol treatment can be considered as baseline.

Baseline laboratory and AE grades will not be accounted for in whole treatment safety analyses.

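### Sections 7.2.5 and 16.5.1.4 contradict each other on who performs the central imaging review; if 7.2.5 is followed, the secondary central estimates for Group C are not an independent check

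*Combined protocol and SAP*

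**What the plan says.** Section 16.5.1.4 describes the central review in these terms: "A Blinded Independent Central Review (BICR) will be organized retrospectively to review all collected scans in this study". It adds that "BICR ensures an independent evaluation of patient scans in a specific study by experts in the specific imaging modality". On blinding it says "The BICR will remain blinded regarding the treatment group of the patients", and that "the reviewers will be blinded regarding the site's assessment which will only be unblinded to the study coordinator". Details are left to a further document: "please refer to the Central Review Charter, that will be provided as a separate guidelines document".

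Section 7.2.5 also describes a retrospective central review of all MRI. It names Vienna, then has a redaction, then continues "study coordinator, study co-coordinator and Tragara pharmaceuticals representative as a secondary analysis". Section 5.1.2 identifies Tragara as the supplier of TG02.

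Section 8.2.2 uses the central data for Group C. After the Kaplan-Meier PFS item it states "These estimates will be presented both based on investigator and centrally reviewed progression data". It says the same for response and duration of response and for the success rate, and it plans a tabulation of differences between local and central PFS times. The items for Groups A and B contain no such statement.

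Sections 7.2.2, 7.2.3 and 7.2.5 make the local RANO assessment the primary measure of progression and response.

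**The concern.** Group C is open-label and every patient receives TG02. Local RANO assessment involves judgement, for example on equivocal progression or T2/FLAIR change. A second read by people who do not know the local result, and have no stake in it, is the natural check on such judgement, and 16.5.1.4 sets out to provide one.

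Section 7.2.5 undoes this in two ways. It puts among the reviewers the one person whom 16.5.1.4 allows to see the site's assessment. It also includes people with a stake in the trial: the supplier's representative, and the coordinator, who supports medical review (9.2.1) and publishes the results (18.1). Agreement between local and central PFS could then reflect shared knowledge rather than corroboration. A reader of the final report would see two sets of estimates and take the second as independent.

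**Working it through.** No figure is in dispute. The plan's own rule is reproduced first, to show where the central review stands in relation to it.

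**Step 1. The Group C rule.** Inputs from section 8.1.1: n = 45, success if at least 13 are progression-free and alive at 6 months, P0 = 20%, P1 = 40%, alpha 0.10, beta 0.05.

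- Exact type I error: P(X ≥ 13), X ~ Binomial(45, 0.20) = 0.0995, within 0.10.
- Exact power: P(X ≥ 13), X ~ Binomial(45, 0.40) = 0.9554, above 0.95.
- One-sided 90% Clopper-Pearson lower limit at 13/45: the 0.10 quantile of Beta(13, 45 − 13 + 1) = Beta(13, 33), which is 0.2002, just above 0.20.

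The design reproduces.

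**Step 2. Whose read feeds the count.** Section 7.2.2 defines PFS by RANO as determined by the investigator, and 7.2.3 and 7.2.5 say the primary measure is local. In 8.2.2 the statement about presenting both sources closes the Kaplan-Meier PFS item, not the preceding item that applies the 13/45 rule. The identity of the central readers therefore changes none of the figures in step 1.

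**Step 3. The two descriptions side by side.**

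| | Section 16.5.1.4 | Section 7.2.5 (legible text) |
|---|---|---|
| Who reviews | Independent imaging experts | Vienna [redacted], both coordinators, a representative of the drug supplier |
| Site assessment | Hidden from the reviewers | Not addressed |
| Study coordinator | The only person unblinded to the site assessment | Named in the review |
| Treatment group | Hidden from the reviewers | Not addressed |

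The third row is the contradiction. The coordinator cannot be both the sole person unblinded to the site assessment and one of the reviewers blinded to it. The first row is a second conflict, on independence. The last row gives little protection in Group C, where all patients receive the same drug.

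**Step 4. What depends on the central read.** From 8.2.2, Group C only: PFS-6, median PFS, response, duration of response, success rate, and the local-versus-central PFS comparison. All are secondary uses.

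**Step 5. Consequence under each reading.** If 16.5.1.4 governs, the review is independent and only the wording of 7.2.5 is wrong. If 7.2.5 governs, the quantities in step 4 lose their independence and the label used in 16.5.1.4 is wrong.

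**The case against.** **The sentence in 7.2.5 is partly redacted.** The words linking Vienna to the roles cannot be seen. A plain list of reviewers is the natural reading, but not a certain one. This stands as a limit; the three roles themselves are legible.

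**Protection is already written.** Section 16.5.1.4 treats the coordinator as distinct from the readers, and the charter may fix membership. This also stands: the documents show that two sections conflict, not that a non-independent review will take place. The protocol text still needs correcting.

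**The central read is secondary.** Correct. A reader might infer that, because 12/45 fails where 13/45 succeeds, slight bias in the central reads could reverse the Group C conclusion. The documents do not support that: central readers cannot move a count built on local assessments. Any one-stage rule also turns on one patient at its cut-off, so this does not measure reader bias.

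**Other safeguards exist.** A reader might take the central review as the only protection against favourable local assessment. That is too strong. RANO sets explicit thresholds, deaths and losses to follow-up before 6 months count as failures, OS-9 and OS-12 need no imaging reader, and scan quality is checked prospectively. None of these replaces an independent second read of progression.

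**Knowledge of the site read is documented for one person.** Nothing says that the co-coordinator or the company representative sees site assessments. For the company representative the issue is interest in the drug, not unblinding.

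**Conclusion.** The inconsistency is real and should be resolved. Its reach is limited to the five secondary central estimates for Group C and the local-versus-central PFS comparison; the 13/45 decision, the sample size and the error rates do not change. No size can be put on possible bias in the central estimates, because the documents give nothing on reader agreement.

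The conclusion assumes that the legible roles in 7.2.5 are reviewers, as the sentence reads, and that the unseen charter does not already exclude them. Section 16.5.1.4 gives no time at which the coordinator is unblinded. If the charter holds the site assessment back until the central reads are complete, the knowledge problem disappears, but the question of independence remains. No actual bias is alleged, and the company's interest is inferred from its role as supplier.

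**What to change.** Amend 7.2.5 to match 16.5.1.4 and align the Central Review Charter with both. Three statements are enough:

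- Only independent imaging-expert readers, blinded to the site's assessment, read and adjudicate scans.
- The study coordinator, the co-coordinator and the company representative neither read nor adjudicate.
- Those three see central results only after the reads are locked.

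The review is retrospective, so the change does not touch patient procedures, the sample size or the decision rule. The cost is wording in the protocol and the charter, provided the independent readers foreseen in 16.5.1.4 are already in place. Their number cannot be seen from the documents; if too few remain without the three roles, readers would have to be added.
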